# Clinical Investigation Plan (CIP)

Study Name: VivaSight-DL study (CIS-009)  
 Ethical committee number: S-20180081

CLI-000427

Rev. 02

## 5. DESIGN OF INVESTIGATION

### 5.1 Design of investigation

A randomized, controlled single-centre investigation comparing the VivaSight-DL and the conventional DLT at a teaching hospital. A pilot study including up to 10 subjects will be performed prior to the investigation is initiated (see section 7.1). The investigation will include a total of 50 adult subjects (25 subjects in each group) admitted to department V at OÜH with established indication of single lung ventilation.

The objective of the investigation is to compare the number of times the tube position needs to be verified with a scope and relevant costs between VivaSight-DL and conventional DLT in a cost-effectiveness analysis. Furthermore, procedure time, intubation attempts and repositioning will be assessed (see section 4. End Points).

The study will start to recruit subjects within four weeks after Ethical Committees approval and nine months ahead or until 50 subjects have been recruited. If the number of subjects cannot be included in time, the sponsor and Principal Investigator will decide if the study should be closed.

Each subject enrolled in the investigation can only participate in the investigation once. The study duration for each subject is counting from the indication of the need of a single lung ventilation procedure until the subject has completed the questionnaire. Only one test device should be used per subjects (VivaSight-DL or conventional DLT).

Only subjects who can be clinically evaluated as eligible for a single lung ventilation procedure i.e. complies with the listed inclusion and exclusion criteria may be included in the investigation. If subjects or their legal representatives do not consent to the investigation or if the subject is not assigned a novice physician to perform the procedure, the procedure will be performed regardless – however off this investigation. A Case Report Form (CRF, appendix III) must be filled in for each subject that is assigned a novice physician to perform the intubation and has signed the Informed Consent (appendix II), and therefore is included in the investigation. After the surgery the subjects will be asked to answer a questionnaire regarding health-related life quality and side effects from the procedure (appendix IV). If the subject cannot give feedback, the reason is stated in the questionnaire.

Physicians with experience in less than 50 DLT placements in patients are included in the investigation. The learning curve is accounted for by giving all physicians a training in performing DLT intubation before participating in the study. During the training, the physicians will perform at least 10 conventional DLT placements and three VivaSight-DL placements in manikin. Investigational product training will be recorded on a separate form and stored in the Sponsor File.

The investigation center is regularly performing single lung ventilations and has a patient flow of minimum 5 per week. The center is willing to allow insight to the departments' general costs in relation to surgeries with single-lung ventilation. The extent of necessary cost data depends on the sites' organisational setup and subsequently the resources spent during single-lung ventilation and reprocessing of bronchoscopes. Data is collected after the entire process related to single-lung ventilation has been thoroughly mapped via monitoring and interviewing key personnel. Cost data related to single-lung ventilation includes but is not excluded to personnel costs, capital costs related to bronchoscopy, reprocessing and performing single-lung ventilation, maintenance costs, cost of service agreements, cleaning verification costs and administrative costs.

### 5.2 Sample size

The pilot study will include a maximum of 10 adult subjects undergoing a surgery with single-lung ventilation

- Maximum 5 subjects using VivaSight-DL
- Maximum 5 subjects using conventional DLT

The study will include 50 adult subjects undergoing a surgery with single-lung ventilation.

- 25 subjects using VivaSight-DL
- 25 subjects using conventional DLT

# Clinical Investigation Plan (CIP)

Study Name: VivaSight-DL study (CIS-009)  
 Ethical committee number: S-20180081

CLI-000427

Rev. 02

## 5.3 Expected time schedule

- Initiation visit: Prior inclusion of first subject and pilot study
- Pilot study: within four weeks after ethics committee approval
- First subject in: immediately after pilot study is completed
- Monitor visit: after 3-6 subjects
- Last subject in: within nine months after including the first subject
- Last subject out: within four weeks after last subject is included
- Close-out visit: within four weeks after last subject out

## 5.4 Randomisation

One randomization list will be prepared containing 50 participants. The randomization list is dividing equally the number of participants for the VivaSight-DL group and the conventional reusable DLT group (standard care at the respective centre).

The randomisation list will be created by using the website random.org (<https://www.random.org/lists/>) and repeating the randomization three times. The treatment will be named 1 (=VivaSight-DL), 2 (=conventional DLT) in the list.

Sponsor will prepare envelopes according to the randomisation list. All envelopes will be clearly numbered in succession and the number will act as the subject number in the investigation. The Investigator will draw an envelope in successive order after the informed consent is obtained from the subject and a physician with experience in < 50 DLT placements in patients is assigned for the procedure. If additional subjects are to be included, the number of subjects must correspond to at least one block. Ambu will supply the additional envelopes.

# 6. TEST PARTICIPANTS

## 6.1 Inclusion criteria for subjects

- Oral explanation of the investigation and Patient Information has been given to the subject or legal representative
- The subject or legal representative has signed the Informed Consent
- The subject is admitted at OUH, department V, section BTY
- Subjects evaluated as eligible for single-lung ventilation with the use of a left sided DLT
- Subjects > 18 years of age

## 6.2 Exclusion criteria for subjects

- Subjects with known tracheobronchial anatomic anomalies
- Subjects going for emergency procedures
- Subjects with anticipated difficult airways
- Subjects with known tracheal pathology
- Subjects requiring rapid sequence induction
- Surgeries in which other lung isolation devices or techniques may be warranted (e.g. tracheostomy, nasal intubation, bronchial blockers)
- Subjects who cannot be intubated with a double-lumen tube (VivaSight-DL or conventional DLT)
- Subjects requiring a right-sided DLT
- Subjects who had participated in the study before

## 6.3 Inclusion criteria for physicians

- Physicians with experience in < 50 DLT intubations in patients
- Physicians who has completed the training course and has experienced at least 10 conventional DLT placements and three VivaSight-DL placements in manikin

# Clinical Investigation Plan (CIP)

Study Name: VivaSight-DL study (CIS-009)  
Ethical committee number: S-20180081

CLI-000427

Rev. 02

## 6.4 Recruitment

The subjects included in this investigation will be under treatment in department V at OÜH, and clinically judged by the investigator to be eligible for a single-lung ventilation. The subject, or if the subject is unable to, the subject's legal representative, will receive information orally and in writing about the investigation (see Patient Information, appendix I) from an Investigator (nurse or physician with at least two years of experience in anesthesia). Patient Information will be given in the pre-anaesthesia room, where the Investigator, the subject and the subjects relatives can discuss the study in privacy and undisturbed. If the subject agrees to participate they must sign the Informed Consent (see Informed Consent, appendix II) before start of the investigation.

A subject is considered included in the investigation as soon as informed consent has been signed. If subject or their legal representative do not consent to the investigation the procedure will be performed regardless, however off this investigation.

When a subject is included the Investigator assures that the subject meets all inclusion criteria and none of the exclusion criteria, by checking the relevant boxes in the CRF.

Participation in the investigation is voluntary and the subject or the subject's legal representative can at any time withdraw from the investigation without any consequence for further examinations and treatment.

If a subject withdraws from the investigation the subject will be replaced to ensure that the total number of subjects included in the analysis reach 50 subjects. If any data was recorded before withdrawal, this will be stored in the investigator binder but not used for analysis. When a subject is replaced the new subject is given a new subject number.

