### 7.9 Awakening of subject and follow up

Immediately after the surgery, the physician is asked to complete a questionnaire regarding the procedure just performed (Appendix VI).

All subjects are woken up immediately after surgery. Within forty-eight hours after the surgery, the subject will be contacted (in the hospital room or over the phone) by a research assistant who will ask questions regarding the subject's health-related life quality and potential side effects from the intubation (Appendix V). It will be the same research assistant who contacts all subjects in order to ensure identical data collection across subjects.

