#### 18.3.2 Handling of dropouts and missing data

Data from intermediate dropouts, who has been intubated but not undergone surgery will not be included within the analysis of the primary outcome. Furthermore, data from intermediate dropouts will be included until dropout. Early dropouts, who dropout prior to intubation will be excluded from all analysis.

Potential missing data points will be explored and substituted via regression imputation or listwise deletion as appropriate. Using substitutions via regression imputation the existing variables are used to make predictions for the missing values. As a result, the data is retained, and significant altering of the standard deviation is avoided. To examine whether potential missing data points are missing at random, or whether they could lead to a potential bias, an independent sample t-test will be applied, comparing the remaining variables of the observations with full data and the observations with missing data.

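### Sections 6.4 and 18.3.2 conflict on data recorded before a withdrawal, and 6.4 alone would discard a complete primary outcome when a subject formally withdraws after extubation

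*Combined protocol and SAP*

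**What the plan says.** Section 6.4 places no time limit on withdrawal. Its sentence covers the subject and continues: "the subject's legal representative can at any time withdraw from the investigation without any consequence for further examinations and treatment". On data already collected it says: "If any data was recorded before withdrawal, this will be stored in the investigator binder but not used for analysis". It then refills the sample: "If a subject withdraws from the investigation the subject will be replaced to ensure that the total number of subjects included in the analysis reach" the target of 50.

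Section 18.3.2 sorts dropouts by stage:

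- Before intubation: "Early dropouts, who dropout prior to intubation will be excluded from all analysis".
- Intubated without surgery: "Data from intermediate dropouts, who has been intubated but not undergone surgery will not be included within the analysis of the primary outcome".
- For the same intermediate group, on everything else: "Furthermore, data from intermediate dropouts will be included until dropout".

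It has no category for a subject who leaves after surgery.

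Section 6.5 adds a third rule. Among its reasons for exclusion is the subject deciding to stop, and once the procedure has started it has only the reason for exclusion entered in the CRF.

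On timing, section 4 counts fibreoptic confirmations over intubation and surgery, and section 7.6 ends the surgery period when the tube leaves the mouth. Section 5.1 runs participation "until the subject has completed the questionnaire", and section 7.9 places that contact after the operation: "Within forty-eight hours after the surgery, the subject will be contacted (in the hospital room or over the phone) by a research assistant".

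**The concern.** A subject is still in the study for up to about two days after the last primary-outcome event can occur. If that subject withdraws in this interval, section 6.4 removes a randomised, fully observed procedure from the primary comparison because of a decision taken after the procedure, with the result already on the CRF.

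The plan describes no blinding, and section 18.2 has all data analysed internally by the sponsor. Section 18.3 defines no intention-to-treat or other named analysis set, so the dropout sentences largely decide who is analysed. Where they disagree or are silent, the choice may be made after the outcomes are known. Replacing the subject restores the number analysed but not the comparison of the groups as randomised. The same primary outcome is also an effect measure in the cost-effectiveness model of section 18.7, so the ambiguity carries over to that result.

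**Working it through.** **1. The rules compared by time of withdrawal**

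- *Before intubation.* 6.4 does not use the data; 18.3.2 excludes the subject from all analyses. They agree.
- *Intubated, no surgery.* 6.4 uses nothing. 18.3.2 keeps what was recorded up to dropout, such as intubation time, attempts, corrections and repositionings during intubation, but leaves out the primary outcome. This is a direct contradiction on the secondary intubation data. On the primary outcome both sections give the same answer.
- *After extubation, before the questionnaire.* The primary outcome is complete (sections 4 and 7.6). 6.4 discards it. 18.3.2 gives no ground for excluding it but does not mention the case. The loss comes from 6.4 alone.

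**2. The plan's own sample size (section 18.1)**

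Inputs: means 0.37234 (conventional) and 0.01087 (VivaSight); variances 0.23622 and 0.01087; multipliers 1.96 and 1.28.

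- Difference in means: 0.37234 − 0.01087 = 0.36147.
- Sum of variances: 0.23622 + 0.01087 = 0.24709.
- n per arm = 0.24709 × (1.96 + 1.28)² / 0.36147² = 19.852; two arms give 39.70, rounded up to 40.
- Allowing 20% dropout: 40 / (1 − 0.20) = 50.

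Both figures match the plan.

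**3. Power if outcomes were lost and not replaced**

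Power = Φ(0.36147 / √(0.24709 / n) − 1.96), with n per arm:

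- n = 25: Φ(3.636 − 1.96) = 95.3%
- n = 23: Φ(3.487 − 1.96) = 93.7%
- n = 20: Φ(3.252 − 1.96) = 90.2%

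Even with the whole 20% allowance lost, power stays at the 90% target. Under 6.4 the loss would be made up to 50 by replacement anyway.

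**4. Scale of one discarded outcome**

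One subject is 1/50 = 2% of the planned total. To illustrate on the 18.1 means, 25 control subjects have an expected total of 25 × 0.37234 = 9.3085 uses. Suppose one control subject is removed and not replaced, with an assumed count of 0 or 1:

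- Count 1: (9.3085 − 1) / 24 = 0.346, so the difference between arms is 0.335.
- Count 0: 9.3085 / 24 = 0.388, so the difference is 0.377.

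The planned difference is 0.361. These are shifts from one arbitrary removal, not a forecast of bias. Bias arises only if withdrawal is related to the outcome, and nothing in the documents allows that relation to be estimated.

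**The case against.** Three stronger readings are tempting, and the documents do not support them.

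- **Opposite rules on the primary outcome of a late withdrawer.** A reader might infer this from 6.4 and 18.3.2 together. But the sentence in 18.3.2 that keeps data until dropout is written for subjects intubated and not operated on, and their primary outcome is left out under both sections. For a subject who has had surgery, 18.3.2 is silent.
- **A power loss from about 95% to 90%.** This does not arise under 6.4 as written, because withdrawals are replaced until 50 are analysed. Without replacement, 20 per arm would still meet the design target.
- **A missed follow-up call as a withdrawal.** Section 5.1 has the reason recorded when a subject cannot give feedback, and the subject questionnaire has a field for non-completion. The loss needs an actual withdrawal in a short interval, and the documents do not suggest that this is common.

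Two further objections carry weight. The fibreoptic count is recorded while the patient is anaesthetised, so a link between it and a later wish to withdraw is possible but not shown. Nor is the loss untraceable: a replacement gets a new subject number, completion or dropout is a verification item in section 9.2, and section 6.5 has reasons for exclusion entered in the CRF.

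What stands is that 6.4 and 18.3.2 cannot both be followed for intermediate dropouts, and that 6.4 read literally removes complete primary outcomes. Traceability shows that a subject left; it does not settle whether the data count.

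**Conclusion.** The point holds in two separate parts: a direct contradiction over secondary intubation data for subjects intubated but not operated on, and a rule in 6.4 alone that would drop the complete primary outcome of a randomised subject who formally withdraws after extubation. It should be fixed, because it leaves the analysis population ambiguous and permits exclusion after randomisation with the outcome known.

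The expected effect is probably small. Each such withdrawal is 2% of 50, the number is unknown, and power is not the issue. The conclusion assumes that 6.4 would be applied literally. The power figures and the illustration also rest on the 18.1 inputs, which describe bronchoscope use to correct placement. Since 7.5.2 and 7.6 make bronchoscopy a routine step in the control arm, the real counts may differ. The consent and patient information were not available to this review, so what they say about data already collected is unknown.

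**What to change.** Adopt one rule for each time of withdrawal and state it identically in 6.4, 6.5 and 18.3.2, before any outcome data are examined:

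- Withdrawal stops further data collection. Data recorded up to that point are kept and analysed in the allocated arm, as far as the consent allows.
- Before intubation: no outcome data, as 18.3.2 already has it.
- Intubated but not operated on: intubation data enter the secondary analyses; the primary outcome is left out, as in 18.3.2.
- After the tube has been removed: the primary outcome is complete, and the subject stays in the primary analysis even if the questionnaire is declined or the subject withdraws.
- Bring the 6.5 instruction on CRF entries after exclusion into line with this.

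In the same edit, say what 50 means: 18.1 treats it as 40 plus a dropout allowance, while 6.4 treats it as the number analysed after replacement. Report withdrawals by arm and by stage.

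Check that the consent text agrees with the rule. The cost is a wording change in three sections and possibly one sentence on retained data in the consent or patient information, with no new procedures or visits. If the existing consent promises that data will not be used after withdrawal, that promise governs for subjects already enrolled, and the affected cases should be reported.

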## 6.5 Exclusion during the examination

The subject can be excluded during the investigation if:

- The subject or legal representative decides to abort the study
- The subject is assigned to a physician with experience in > 50 DLT intubations in patients
- The investigator considers it necessary to change the type of endotracheal tube used for the procedure
- The investigator assess that it is necessary to exclude the subject from the investigation to ensure safety of the subject

If a subject withdraw from the study before the study randomization envelopes seal is broken (example no. 10), then the next subject will continue with consecutive subject number (no. 11).

If the subject is excluded *after* the procedure is started, he or she will be treated and receive routine treatment. Reason for exclusion will be stated in the CRF but otherwise data will not be collected in the CRF.

If the subject is excluded *before* the procedure is started, he or she will receive routine treatment. Reasons for exclusion will be stated in the CRF but otherwise data will not be collected in the CRF.

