### 12.2 Informed Consent

Informed Consent (appendix II) is the voluntary confirmation and documentation of the willingness of a subject to participate in a particular investigation, after information has been given orally and in writing to the subject. Point of enrolment is from the time when informed consent is signed. The subject and Investigator must each sign and date the Informed Consent. The subject can be excluded from the study after Informed Consent is obtained in if the subject is assigned a physician with experience in > 50 DLT intubations in patients. This is done, as the subject is not assigned a physician until earliest the day before the surgery. To ensure that the subject has sufficient time to consider participation the Patient Information is given at the preparation meeting which can take place before a physician is assigned.

The Investigator signs to confirm that information has been given to the subject. One copy is for the subject and the other one for the Investigator binder.

A draft version of the Informed Consent is attached to the CIP. A final copy of this Informed Consent must be provided to the Sponsor prior to first use.

Participation in the investigation is voluntary and the subject can at any time chose to be withdrawn from the investigation. This will not have consequences on his/her treatment.

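### Section 6.5 passes over an unopened envelope when a subject withdraws, so one such withdrawal leaves the 50-envelope list unable to give exactly 25 per arm, and the block that governs the top-up is undefined

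*Combined protocol and SAP*

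**What the plan says.** - Section 5.4 sets up a single list: "One randomization list will be prepared containing 50 participants". It is divided equally between the arms, which matches the 25 per arm in sections 5.1 and 5.2.
- Section 5.4 merges two identifiers: "All envelopes will be clearly numbered in succession and the number will act as the subject number in the investigation".
- Section 5.4 fixes when an envelope is drawn: "after the informed consent is obtained from the subject and a physician with experience in < 50 DLT placements in patients is assigned". Section 7.3 gives the same order: a subject with an experienced physician is excluded, and a subject with a novice is randomised.
- Section 6.5 deals with a subject who withdraws "before the study randomization envelopes seal is broken (example no. 10), then the next subject will continue with consecutive subject number (no. 11".
- Section 5.4 allows for a top-up: "If additional subjects are to be included, the number of subjects must correspond to at least one block". It adds that the sponsor supplies the extra envelopes.
- Section 6.4 replaces withdrawn subjects, under new numbers, until 50 are analysed.
- On timing, section 6.4 states: "A subject is considered included in the investigation as soon as informed consent has been signed". Section 12.2 explains why some consented subjects are later excluded: "This is done, as the subject is not assigned a physician until earliest the day before the surgery". The plan has no separate screening number.

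**The concern.** When the envelope number is also the subject number, moving on to the next number means moving on to the next envelope. The sealed envelope of the withdrawn subject is set aside together with the allocation inside it. A list built to hold exactly 25 of each treatment keeps that property only if every envelope is used.

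Three things are at stake: the stated 25 per arm, the supply of envelopes, and a simple audit trail in which each envelope corresponds to one randomised subject. The plan's remedy is to add envelopes in units of a block. Section 5.4 describes one randomised list of 50, with no blocks and no block size, so the site and the sponsor cannot tell from the plan how many envelopes to add or how they are balanced.

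It is also unclear when a number is taken. Section 5.4 ties it to the envelope, after a novice is assigned. Section 6.4 counts inclusion from consent, the Patient Registration List in 11.1 is pre-printed with ranked numbers, and the CRF shows the subject number beside the enrolment date.

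**Working it through.** **1. The plan's own sample size.** From section 18.1: means 0.37234 and 0.01087, variances 0.23622 and 0.01087, z-values 1.96 and 1.28.

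n per arm = (0.23622 + 0.01087) × (1.96 + 1.28)² / (0.37234 − 0.01087)² = 19.852

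The total is 39.70, rounded to 40. Allowing for 20% dropout, 40 / 0.80 = 50. The plan's figures reproduce.

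**2. One skip.** The list holds 25 + 25 = 50. Discarding one envelope leaves 49, split 25:24. No skip count of 1 or more leaves 25:25.

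**3. Several skips, initial list only.** The documents do not say how many withdrawals fall before the seal is broken, so k = 1 to 10 is an assumption. An unopened envelope is skipped without knowledge of its content. The number of skips from one arm, x, is therefore hypergeometric: P(x) = C(25, x) × C(25, k − x) / C(50, k). The arms that remain differ by |k − 2x|.

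- Equal arms at k = 10: C(25,5)² / C(50,10) = 53,130² / 10,272,278,170 = 0.275.
- Power is Φ(0.36147 / √(0.23622/n_DLT + 0.01087/n_Viva) − 1.96), averaged over x.

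| Skips k | Randomised | Mean arm difference | P(difference ≥ 4) | Average power |
|---|---|---|---|---|
| 0 | 50 | 0 | 0 | 95.3% |
| 1 | 49 | 1.0 | 0 | 94.9% |
| 5 | 45 | 1.8 | 5% | 93.1% |
| 10 | 40 | 2.2 | 29% | 90.0% |

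For comparison, an even 20:20 has power 90.2%. If every skip fell in the conventional arm, power would be 90.4% at k = 5 and 81.1% at k = 10. The latter has probability C(25,10) / C(50,10) = 3,268,760 / 10,272,278,170, about 0.0003.

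**4. With the top-up.** Suppose additional balanced blocks are opened only until 50 are randomised. The block size is not in the plan, so sizes 2, 4, 10 and 50 are assumed.

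| Skips k | P(exactly 25:25) |
|---|---|
| 1 | 50% |
| 2 | 38–51% |
| 5 | 26–33% |
| 10 | 20–28% |

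If instead whole blocks are always completed, the imbalance left by the skips is carried forward. With one skip and a block of 2, the result is 49 + 2 = 51 subjects, split 26:25. A balanced block has an even size, so an odd number of skips can never be brought back to exactly 50 this way.

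**5. Which withdrawals count.** Under 5.4 a subject has no number until an envelope is drawn, and drawing comes after a novice is assigned. The skip rule can then apply only between drawing and opening. Section 7.2 lists what is entered at consent, and the subject number is not on that list. Against this stand 6.4, 11.1 and the CRF layout, together with the requirement in 6.5 to record the reason for exclusion in the CRF even when it occurs before the procedure. None of these says that a number is issued at consent, but none rules it out.

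**The case against.** The best defence has four parts.

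- **The plan provides for shortfall.** Extra envelopes and replacement mean 50 subjects can be reached. This stands. A reader might infer that the trial cannot deliver its sample size; the documents do not support that. Only exact 25:25 is lost, and only the meaning of the block is missing.
- **Subjects given an experienced physician draw no envelope.** This stands under 5.4 and 7.3. The skip sentence in 6.5 also speaks of withdrawal, while assignment to an experienced physician is listed separately as a reason for exclusion. A reader might infer from 12.2 that many envelopes are used up by patients who are never randomised. That needs numbers to be issued at consent, contrary to 5.4, and a share of experienced physicians that the plan does not give.
- **The effect on inference is small.** This stands. None of the planned tests in 18.3.3 requires equal arms, and the 20% allowance absorbs about 10 skips on average. Skipping a sealed envelope does not depend on its content, so a reader who infers selection bias goes too far, provided the content cannot be seen. The plan does not state that the envelopes are opaque.
- **Reusing envelope 10 would put two people under one number.** This is true while the two numbers are the same, and 6.5 avoids it. A set-aside envelope with its seal intact can also be accounted for. That is a reason to separate the numbers rather than to discard allocations.

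**Conclusion.** The point holds in a limited form. Sections 5.4 and 6.5 together discard one unopened allocation for each withdrawal before the seal is broken. A single such withdrawal makes 25:25 impossible from the list of 50. The top-up can restore the total but not assured balance, and it refers to a block that does not exist in the plan.

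The size is modest. On the plan's planning values and a normal approximation, average power falls from about 95% with no skips to 93% with 5 and 90% with 10, before any top-up. The chance that the arms differ by 4 or more is 5% and 29% in the last two cases. The skip counts and block sizes are assumed; the documents give neither. The harm is chance imbalance, list attrition and a less clean audit trail. The stated sample size is not wrong.

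Withdrawals after opening, with replacement, also disturb 25:25. That is a separate matter and is not counted here.

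**What to change.** - Give a screening number at consent, and use it in the CRF and the Patient Registration List.
- Assign the randomisation number only when the envelope is opened, after a novice physician is confirmed. State this in 5.4 and make 6.4 agree, so that the timing is settled.
- Replace the rule in 6.5 with: an envelope whose seal is unbroken is used for the next randomised subject.
- Have the sponsor generate a reserve list in advance, in balanced blocks of a size held by the sponsor, and let the top-up sentence in 5.4 refer to that list.

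With the third change, the initial 50 envelopes give exactly 25:25 randomised. The cost is wording in 5.4, 6.4 and 6.5, one CRF field and a few reserve envelopes prepared at the start.
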